where ΔW_{R-F} is the same variable as in model (1), based on imputed 30-month weights and $[XI]_i$ represents the interaction between a covariate X and indicator for treatment group I_k . The first step is to test whether the parameters on the interaction, γ_i , are all 0.¹⁶⁰ If this hypothesis is not rejected, modeling stops here. If this hypothesis is rejected, then the second step is to test whether the parameters on the interaction, γ_i , are the same across groups. The form of this model is

$$\Delta W_{R-F} = \beta_0 + \beta_1 PC + \beta_2 IT + \beta_3 \Delta W_{E-R} + \beta_4 W_E + \eta X + \sum \gamma_i I [XI_k]_i + \sum \alpha_i S_i + \sum \delta_i E_i + e_{ij} \quad (4)$$

where ηX represents the main effect of the covariate. If this test is not significant, modeling can stop here or, if desired, the term $\sum \gamma_i I [XI_k]_i$ can be dropped from the model and the estimate of treatment effects adjusted for the main effect of the covariate can be obtained. If the test is significant, this indicates that treatment effects are different for different values of X . For a categorical covariate, the estimates of treatment effects are obtained within each level of the covariate. For a continuous covariate, estimates will be obtained at several selected values of the covariate, e.g. 25th, 50th, and 75th percentiles of the covariate. These estimates are obtained using model (3). We will use two-sided 0.05 tests on the regression coefficients.

Aim 8. Determine **process variables** that are associated with sustained weight loss [e.g., physical activity, dietary intake of various nutrients (e.g., fats), and food groups (e.g., fruits and vegetables)].

This analysis will be carried out by the same methods described above for the primary analysis with a priori covariates measured at baseline.

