Detectable Effects: Difference in ΔW_{R-F} between active treatment (PC and IT) and control (SD/UC) in kg, for powers 0.8, 0.85, 0.9 under various assumptions about the SDE (standard deviation of the estimate) and sample size. Figures for subgroups assume that the primary analysis will be in the expected direction.

Detectable effects/sample size

The sample size for the WLM trial (800 randomized participants) was designed to provide adequate power for subgroup comparisons as well as for the overall study comparisons. In particular, the trial has 90% power to detect about a 2.0 kg difference in weight change between either of the active intervention groups (PC or IT) and the self-directed group overall, and 80% power to detect treatment differences of about 2.7 kg among African Americans.

Because randomization occurs after the initial 5-month weight-loss phase of the trial, the sample size calculations are based on the number randomized, and not on the number who initially enter the trial. In order to randomize 800, we anticipate that we need 1600 participants to enter Phase I. This estimate assumes the following: 10% of those entering Phase I drop out before the 5 months ends; 35% complete the weight loss phase but fail to lose at least the 4 kg of weight required for randomization, and 5% are eligible but decline to be randomized. These estimates are based on the experience in the PREMIER study in which 6-month follow-up rates were 94%, and 50% of participants had lost 4 kg or more at the 6-month visit.

None of the calculations presented in this section factor in participant dropout following randomization, since we propose an intention-to-treat analysis and will impute data for those individuals who do not complete follow-up. The effect sizes shown in Table 5 should therefore be interpreted as net effect sizes after imputation.

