The method used to estimate detectable effects was as follows. The PREMIER data (as of January 2002) were used for the purpose of estimating the standard deviation of the estimate (SDE) of treatment effects. Among those PREMIER participants who lost at least 4 kg in the first 6 months, their changes (12 mo. vs 6 mo, and 18 mo. vs. 6 mo.) were regressed on their entry weight, the 6-month change, gender, and two treatment group indicators. Thus, both the sampling method and the statistical method used to estimate detectable effects were identical to what we plan for the analysis of the WLM trial. Adjusted to the projected sample size of 800 participants, the SDEs were 0.45 and 0.52 kg, respectively. Since this indicates that the variability might increase with the length of the interval between measurements, the table above includes some values of SDE above 0.52. The table provides the detectable effects (kg) for three

powers (0.8, 0.85, 0.9) for the entire sample, for a 40% subgroup (appropriate for subgroup analysis in African Americans) and for a 60% sample (appropriate for subgroup analysis in women). These effects refer to the primary analysis in the left panel (comparison of weight change ΔW_{R-F} between PC and SD/UC, or between IT and SD/UC, taking the multiple tests into account, at significance level 0.05 two-sided) and the subgroups in the right panels (one-sided tests without multiple testing adjustment). Assuming that the 0.60 row were to be true, the sample size is sufficient to detect an effect in the 1.8-2.1 kg range with power 0.8-0.9 in the entire sample, and to detect effects in the range 2.6-3.0 kg with power 0.8-0.9 in a 40% sample, and effects 2.2 -2.4 kg with power 0.8-0.9 in a 60% sample.

13. Data Management and Quality Control

Data Management System. Data reaches the CC via several routes: distributed entry of eligibility and other data by the sites using a web based system developed by the CC; centralized entry of selected data by the CC; entry of selected intervention information directly by participants via the intervention web site; and secure file transfer of laboratory data using the web based system.

Distributed entry: Data entry is accessible via the web to any computer at the sites via Internet Explorer. Web based data entry systems include sophisticated range and cross checks, and primary outcome data is 100% verified.

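### The 80% power for a 2.7 kg effect in African Americans is for a within-subgroup contrast that Aim 4 produces only after a significant, and less powerful, treatment-by-race interaction test

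*Combined protocol and SAP*

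**What the plan says.** Under Detectable effects/sample size, section 12 says that the sample size "was designed to provide adequate power for subgroup comparisons as well as for the overall study comparisons", and gives "80% power to detect treatment differences of about 2.7 kg among African Americans". Table 5 defines its entries as differences in weight change between an active arm and SD/UC. One panel is "for a 40% subgroup (appropriate for subgroup analysis in African Americans"; another is for a 60% subgroup, meant for women. The text describes "the subgroups in the right panels (one-sided tests without multiple testing adjustment".

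Aim 4 (Secondary Covariate Analyses, Models (3) and (4)) takes a different route. Model (3) adds treatment-by-covariate terms. Step 1 tests whether all of these coefficients are zero: "If this hypothesis is not rejected, modeling stops here". Step 2, in Model (4), tests whether the coefficients are equal across arms. If step 2 is not significant, modelling may end, or the interaction may be dropped and one treatment effect per arm reported, adjusted for the covariate. Effects within each level of a categorical covariate are obtained only if step 2 is significant. On significance levels, the Aim 4 text ends: "We will use two-sided 0.05 tests on the regression coefficients".

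The plan gives no power for the interaction test, and no analysis by race or sex that does not depend on it.

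**The concern.** The sample-size section and the analysis section describe different tests. The power statement is for a contrast inside the African-American subgroup. The analysis produces that contrast only when the data first show that the treatment effect differs by race. An interaction contrast has a larger standard error than a within-subgroup contrast. Its power also depends on how far the two race groups differ, not on how large the effect is in African Americans.

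The background section says that new maintenance strategies must address African Americans specifically, and the recruitment section makes 40% African-American randomization a major goal. If the interventions help both race groups to a similar degree, the plan as written would usually give no separate estimate for African Americans. Estimates that appear only after a significant interaction also tend to exaggerate the difference between subgroups.

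**Working it through.** **Inputs from section 12.** n = 800; African-American share 0.40. PREMIER gave these figures for changes over 6 and 12 months: "the SDEs were 0.45 and 0.52 kg, respectively". The SDE 0.60 row is the one the text uses to illustrate Table 5.

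**Assumptions.** 1:1:1 allocation (no ratio is stated), equal residual variance in both race groups, and no allowance for dropout (the plan's own convention). The effects in other participants are scenarios, because the documents give none.

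**1. What the SDE is.** For the whole sample at 80% power with α = 0.025 two-sided (the first Holm step): (2.241 + 0.842) × 0.60 = 1.85 kg, against 1.8 in Table 5. The SDE therefore acts as the standard error of one active-versus-SD/UC contrast.

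**2. Reproducing the subgroup figure.** The standard error in a 40% subgroup is 0.60/√0.4 = 0.949 kg. Power for 2.7 kg at two-sided 0.05 is Φ(2.7/0.949 − 1.96) = Φ(0.886) = 81%. The stated 80% reproduces.

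**3. Sidedness of the panels.** Detectable effects in the 40% panel at SDE 0.60, for powers 0.80, 0.85 and 0.90:

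| | 0.80 | 0.85 | 0.90 |
|---|---|---|---|
| Table 5 | 2.6 | 2.8 | 3.0 |
| Two-sided 0.05 (one-sided 0.025) | 2.66 | 2.84 | 3.08 |
| One-sided 0.05 | 2.36 | 2.54 | 2.78 |

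The panel follows the two-sided 0.05 critical value.

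**4. Which step decides.** Step 2 releases the within-level estimates. Race is already a main effect in Model (1), so only two treatment-by-race terms can be estimated beside it, and for race step 1 is then the same 2-df interaction test.

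**5. Standard error of the interaction.** 0.60 × √(1/0.4 + 1/0.6) = 0.60 × 2.041 = 1.22 kg. A 60/40 split by sex gives the same value.

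**6. Chance of passing the 2-df test.** The PC and IT contrasts share SD/UC, so their correlation is 0.5. With the same interaction d in both arms, the noncentrality is (4/3)(d/SE)². At SDE 0.60, with 2.7 kg in African Americans:

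| Effect in others (kg) | d (kg) | Noncentrality | Chance of passing |
|---|---|---|---|
| 0 | 2.7 | 6.48 | 62% |
| 1.0 | 1.7 | 2.57 | 28% |
| 2.0 | 0.7 | 0.44 | 8% |
| 2.7 | 0 | 0 | 5% |

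If the 2.7 kg interaction is full in one arm and half in the other, 62% becomes 49%.

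**7. Range over the SDE.** The last column is for one active arm against SD/UC (1 df): (1.960 + 0.842) × 2.041 × SDE.

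| SDE | Within-subgroup power, 2.7 kg | Chance of passing, d = 2.7 kg (2 df) | Interaction detectable at 80% |
|---|---|---|---|
| 0.45 | 97% | 87% | 2.6 kg |
| 0.52 | 91% | 75% | 3.0 kg |
| 0.60 | 81% | 62% | 3.4 kg |
| 0.70 | 68% | 48% | 4.0 kg |

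**8. Achieved enrolment.** The Phase III rationale reports 1032 participants, 38% African American. Rescaling, SDE = 0.60 × √(800/1032) = 0.528 and the interaction standard error is 0.528 × √(1/0.38 + 1/0.62) = 1.09 kg. Within-subgroup power becomes 88%. The four chances in step 6 become 73%, 35%, 9% and 5%.

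**The case against.** **The power figure is correct for what it names.** A reader might infer that the 80% is miscalculated, or that it was offered as power for an interaction. Neither is supported: the text and the Table 5 caption describe an active-versus-control difference, and the number reproduces. What is missing is a planned analysis that delivers that contrast.

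**The sentence that stops modelling is step 1.** A reader might treat it as the whole obstacle. In general, Model (3) as printed has no separate main effect of the covariate, so step 1 can be read as asking whether the covariate matters in any arm. On that three-slope reading, with no race difference in SD/UC, step 1 passes 97% of the time for a 2.7 kg interaction in both active arms. Step 2 still decides: the chance of passing both steps is 62% for d = 2.7 kg, 17% for d = 1.35 kg and 3% for d = 0.

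**Equal benefit is where a separate estimate matters least.** If everyone gains 2.7 kg, the primary test has z = 2.7/0.60 = 4.5 against 2.24, or about 99% power, and the pooled effect covers African Americans too. This stands as a limit on the consequence. It does not make the subgroup power statement relevant to the analysis that would be run.

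**Testing interaction first guards against spurious subgroup claims, and Aim 4 is secondary.** This also stands for claims that the effect differs between groups. It is not a reason to withhold estimates and intervals.

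**The one-sided wording could look like a numerical error.** It is not one: no one-sided level is given, and one-sided 0.025 has the same critical value as two-sided 0.05. The match is also only approximate in places; the 60% panel at SDE 0.40 and power 0.90 prints 1.5 against 1.67 computed. This is a labelling point.

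**Conclusion.** The concern holds. Section 12 cites power for a within-race contrast, and Aim 4 yields that contrast only after a significant treatment-by-race interaction. At SDE 0.60 and n = 800, the 81% within-subgroup power compares with a chance of about 62% that the estimate is produced at all if others gain nothing, and 28%, 8% or 5% if they gain 1.0, 2.0 or 2.7 kg.

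The size of the loss is not fixed. It is about 20 points when the whole effect is confined to African Americans, and much larger when both groups benefit. With the smaller PREMIER SDE of 0.45 and a 2.7 kg interaction, the chance of passing is 87%, so a general statement that the interaction test always falls below 80% would be wrong. The figures assume 1:1:1 allocation, equal residual variance, and the same interaction in PC and IT. The primary analysis is unaffected.

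**What to change.** For race and sex, the subgroups that Table 5 covers, report PC minus SD/UC and IT minus SD/UC with 95% confidence intervals in each level. Take them from the interaction model whatever the interaction result, and print the interaction p-value beside them. Any claim that the effect differs between subgroups should still rest on the interaction test.

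In section 12, label the 40% and 60% panels as within-subgroup power. State the interaction detectable with 80% power (2.6, 3.0, 3.4 and 4.0 kg at SDE 0.45, 0.52, 0.60 and 0.70, n = 800). Reconcile the one-sided description of the panels with the two-sided 0.05 tests in Aim 4, noting that the panels match the two-sided 0.05 critical value.

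The Phase III plan already refers to the results of the first two phases, so the added estimates should be marked as specified after those results. The cost is some plan wording, a few table rows, and a less favourable stated power for detecting subgroup differences. No new data are needed.

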- *Medical Outcomes Study Short Form Health Survey (SF-36)*, 9 subscale scores (physical function, role function-physical, role function-emotional, bodily pain, general health, social function and psychological well-being /mental health, vitality health transition, and side effects checklist), plus overall scores for mental and physical well being;
- *Social Support and Eating Habits Survey* (2 subscores each for family, friends, total 4 scores);
- *Social Support and Exercise Survey* (2 subscores for family, 1 for friends, total 3 scores);
- *Perceived Stress Scale (PSS)* (4-item subset of the 14-item scale, 1 score);
- *Patient Health Questionnaire (PHQ-8)*, 1 score).

3. Prevalence of CVD risk factors:

The sample will be stratified based on baseline information into positive for the condition (i.e., medication treated or elevated) vs. neither.

- *Hypertension*: Individuals with prevalent hypertension (elevated BP or taking an antihypertensive medication at baseline) will be scored for improvement (0, neither of these is true at time F) vs. persistent hypertension (1). Individuals without hypertension at baseline will be scored as incident hypertension (1, defined by either elevated BP or taking an antihypertensive medication at time F) or persistent non-hypertension (0).
- *Hyperlipidemia*: Individuals with prevalent hyperlipidemia (fasting LDL-C \geq 130 mg/dl or taking lipid-lowering medication at baseline) will be scored for improvement (0, neither of these is true at time F) vs. persistent hyperlipidemia (1). Individuals without hyperlipidemia at baseline will be scored as incident hyperlipidemia (1, fasting LDL-C \geq 130 mg/dl or taking lipid-lowering medication) or persistent non-hyperlipidemia (0).
- *Diabetes*: Individuals with prevalent diabetes (fasting glucose \geq 125 mg/dl at baseline or self-diagnosis of diabetes) will be scored for improvement (0, fasting glucose $<$ 125 mg/dl) vs. persistent diabetes (1). Individuals without diabetes at baseline will be scored as incident diabetes (1, fasting glucose \geq 125 mg/dl or taking diabetes medication) or persistent non-diabetes (0).

Design Variables

1. Treatment:

There are three treatment groups, parameterized so that SD/UC is the reference group.

2. Sites:

There are four sites. Portland will be coded as the reference group.

Primary Covariates

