The trial’s primary specific aim is to compare the effectiveness of each of two active interventions (PC and IT) versus self-directed/usual care in maintaining weight loss from randomization (R, at the end of the initial Phase I weight-loss phase of the trial) to the end of Phase II maintenance (F), 30 months post randomization. We use E to denote an entry measure (beginning of weight-loss program, or Phase I), e.g. W_E .

Formal hypotheses:

Null hypothesis: The PC [IT] intervention does not differ from SD/UC in the change in weight over the 30-months maintenance period; this is a joint hypothesis with two parts: $\beta_1 = 0$ and $\beta_2 = 0$.

Alternate hypothesis 1. The PC intervention differs from SD/UC in the amount of weight change over the 30-months maintenance period: $\beta_1 \neq 0$ (2-sided test).

Alternate hypothesis 2. The IT intervention differs from SD/UC in the amount of weight change over the 30-months maintenance period: $\beta_2 \neq 0$ (2-sided test).

The full model for the primary hypothesis test is

$$\Delta W_{R-F} = \beta_0 + \beta_1 PC + \beta_2 IT + \beta_3 \Delta W_{E-R} + \beta_4 W_E + \sum \alpha_i S_i + \sum \delta_i E_i + e_{ij} \quad (1)$$

where PC is an indicator of the personal contact intervention; IT is an indicator of the Web-based intervention; ΔW_{E-R} indicates the change in weight from Entry to Randomization, and W_E is the Entry weight. The S_i terms are indicators of the performance sites, the E_i terms are planned additional explanatory variables, and e_{ij} is a random “error” term assumed to be normally distributed with mean zero. The additional explanatory (E’s) factors are 1) age, 2) female gender, 3) African-American ethnicity, and 4), gender x ethnicity interaction.

Under this model, β_1 represents the effect, after adjusting for all of the explanatory factors, of the PC intervention vs. SD/UC, and β_2 represents the corresponding contrast for the IT vs. SD/UC groups. Tests of the null hypotheses that $\beta_1 = 0$ and $\beta_2 = 0$ are thus the test of the primary hypothesis. Because the PC vs. IT contrast is a secondary aim, a test of the null hypothesis that $\beta_2 - \beta_1 = 0$ is done only if at least one of the previous two null hypotheses is rejected.

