Finally, in the stratum of individuals without the risk factor at baseline, we will evaluate the relative risk of developing the risk factor (incident cases, defined by medication use or elevation of the corresponding physiologic measurement). We will compare arms within each stratum using a chi-square test.

Aim 6. Compare the effects of PC, IT, and SD/UC on measures of behavior change (e.g., physical activity, aspects of diet).

The following alternative hypotheses will be evaluated against the null hypothesis of no difference between treatment group and SD/UC.

- The PC intervention produces greater behavior change than does SD/UC
- The IT intervention produces greater behavior change than does SD/UC

Aim 7. Compare the effects of PC, IT, and SD/UC on weight change **from entry** (prior to Phase I) to the end of the post-randomization maintenance phase (Phase II).

While change in weight from R to F is of primary interest, comparison of the change in weight from initial entry (E) to final assessment (F) is an additional study aim. The logic behind this aim is that, if the maintenance interventions are successful in maintaining all or some of the original weight loss, then some of the original weight loss should persist to some extent through the end of the trial. The analytic model for this analysis is

$$\Delta W_{E-F} = \beta_0 + \beta_1 PC + \beta_2 IT + \beta_4 W_E + \sum \alpha_i S_i + \sum \delta_i E_i + \varepsilon, \quad (2)$$

using the same conventions and statistical approaches as for Model 1. The imputed 30-month weights will be used in this analysis.

Secondary Covariate Analyses

The analyses in this section are motivated by an interest in factors that may moderate weight loss in the various treatment groups.

Aim 4. Compare the effects of PC, IT, and SD/UC on weight maintenance in **subgroups defined by race, sex, age, and baseline body mass index.**

Comparison of treatment effects across subgroups defined by race, sex, age, baseline body mass index, and potentially additional factors, will be approached using the same analytic model (1), with added terms to elucidate possible differential effects between subgroups, operationalized as interactions between treatment group indicators and subgroup indicators. The model is:

$$\Delta W_{R-F} = \beta_0 + \beta_1 PC + \beta_2 IT + \beta_3 \Delta W_{E-R} + \beta_4 W_E + \sum \gamma_i [XI_k]_i + \sum \alpha_i S_i + \sum \delta_i E_i + e_{ij} \quad (3)$$

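### The Aim 4 subgroup procedure does not say which arms its interaction terms cover; under the SAP's stated coding, step 2 misses effect modification shared by PC and IT, and Model (3) estimates for baseline BMI can be biased

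*Combined protocol and SAP*

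**What the plan says.** All of this is in section 12 (Statistical Analysis Plan).

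- **Coding.** Under Design Variables: "There are three treatment groups, parameterized so that SD/UC is the reference group". Models (1), (3) and (4) accordingly carry a PC and an IT indicator and none for SD/UC.
- **Subgroup terms.** Under Aim 4, differential effects are "operationalized as interactions between treatment group indicators and subgroup indicators". The added term "represents the interaction between a covariate X and indicator for treatment group" I_k. The range of k is not given.
- **Factors.** The aim is introduced as "Comparison of treatment effects across subgroups defined by race, sex, age, baseline body mass index, and potentially additional factors". The Specific Aims (section 2) also list CVD risk factors.
- **Main effects already present.** In Model (1), the additional explanatory "factors are 1) age, 2) female gender, 3) African-American ethnicity, and 4), gender x ethnicity interaction". Baseline BMI is not among them.
- **Step 1.** In Model (3), test that all gammas are zero. "If this hypothesis is not rejected, modeling stops here".
- **Step 2.** In Model (4), which adds a main effect for X, test whether the gammas "are the same across groups". If not significant, the interaction may be dropped and the main effect kept. If significant, subgroup effects are reported, and "These estimates are obtained using model (3".

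**The concern.** The only treatment indicators that the SAP defines are PC and IT. An analyst who builds the interactions from them has two gammas, and equality of two gammas is a comparison of PC with IT. It is not a test of whether either effect against control varies with X. If both interventions worked less well in, say, African Americans, the two gammas would be alike, step 2 would not reject, and the interaction could be dropped.

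The same analyst, examining BMI, would take the reported effects from a model in which BMI has no slope in the control arm.

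An analyst who gives all three arms a slope gets the ordinary interaction test and valid estimates. Two competent readers could therefore reach opposite Aim 4 conclusions from the same data. This matters because section 12 says that the sample size was chosen to give adequate power for subgroup comparisons.

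**Working it through.** The documents give no power or error rate for this procedure, so there is no stated figure to reproduce. I calibrated to Table 5 and compared the two readings.

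**Inputs**
- From section 12: 800 randomized; SDE 0.60 kg, the row that the text discusses; two-sided 0.05 tests.
- Assumed: 267 per arm, X standardized, and the slopes below.

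**Calibration.** At two-sided 0.025, 0.60 x (2.241 + 0.842) = 1.85 kg and 0.60 x (2.241 + 1.282) = 2.11 kg. Table 5 gives 1.8 and 2.1, so SDE is the standard error of an arm contrast. Residual SD = 0.60 / sqrt(2/267) = 6.93 kg, and n/SD² = 267/48.06 = 5.556.

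Write b for the slope of weight change on X in an arm. The direct 2-df test has noncentrality 5.556 x (sum of squared deviations of the three slopes from their mean). Powers from this formula are large-sample; simulated values use 3,000 trials per setting unless noted.

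**1. Step 2 with two indicators, modification shared by PC and IT**

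| Slopes SD/UC, PC, IT (kg per SD) | Sum of squares | Noncentrality | Direct test, formula | Direct test, simulated | Two-step, simulated |
|---|---|---|---|---|---|
| 0, 1.5, 1.5 | 1.5 | 8.33 | 0.74 | 0.73 | 0.05 |
| 0, 2, 2 | 2.667 | 14.8 | 0.94 | 0.94 | 0.05 |

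The PC-minus-IT contrast is zero in both rows, so step 2 rejects only at its 5% level, whether or not X is already in the model. For a 40% binary subgroup with both effects 4 kg different, the simulated figures are 0.04 against 0.93.

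**2. Model (3) estimates with two indicators, X not among the explanatory factors**

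The PC x X coefficient then estimates b_PC rather than b_PC - b_SD. The 25th and 75th percentiles of X lie 1.349 SD apart, so the change in PC effect between them is reported as 1.349 x b_PC instead of 1.349 x (b_PC - b_SD). The bias is 1.349 x b_SD.

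- Main effect only (1, 1, 1): reported 1.35, true 0 (simulated 1.36; 0.84 if X correlates 0.8 with entry weight, which is in the model).
- Control slope only (2, 0, 0): reported 0, true -2.70 (simulated -0.01; a fit with the main effect gives -2.73).
- Main effect plus PC-only modification (1, 3, 1): PC reported 4.05, true 2.70; IT reported 1.35, true 0. Both steps are significant in about 90% of simulated trials, and in those the averages are 4.1 and 1.3 (3.6 and 0.8 with the 0.8 correlation). The biased values are therefore ones that the plan would report.

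**3. Three slopes**

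Model (3) is then the same fit as Model (4), and step 2 is the 2-df interaction test. Shared modification of 1.5 kg per SD is found with probability 0.73, as with the direct test.

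What remains is the gate. For X not among the explanatory factors, step 1 has 3 df and noncentrality 5.556 x (sum of squared slopes). With slopes 1, -0.5, -0.5 the mean is zero and both tests have noncentrality 5.556 x 1.5 = 8.33. The 3-df test has power 0.67 against 0.74 for the 2-df test, so passing both steps cannot exceed 0.67. Simulated values are 0.64 to 0.65 for the two-step procedure against 0.73 directly.

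**4. Final false-declaration rate, main effect only (1 kg per SD)**

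Step 1 rejects often: about 85% with two indicators and 94% with three slopes. Step 2 follows, and interaction is finally declared in about 3% to 6% of trials under either reading.

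**The case against.** The strongest reply is that the authors meant three slopes. The text names three treatment groups. It writes PC and IT for the treatment effects but switches to I_k for the slopes. It also treats equal gammas as equivalent to a plain main effect, which is true only if every arm has a slope. On that reading step 2 is correct and Model (3) merely reparameterizes Model (4). This stands, and it limits the point to an ambiguity that does harm under one reading. It does not remove the ambiguity: the range of k is unstated, and the only indicators that the SAP defines are PC and IT.

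Three stronger conclusions are tempting, and the documents do not support them.

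- **That the procedure fails on either reading, because three slopes duplicate main effects already in the model.** The redundant column leaves the fit, the within-subgroup treatment contrasts and the F tests unchanged. With X among the explanatory factors and a 4 kg difference in a 40% subgroup, the two-step and direct procedures both reject 93.9% of the time.
- **That main effect and interaction are confused for every subgroup.** Race, sex and age already have main effects through the explanatory terms. Only baseline BMI and other added factors, such as CVD risk factors, are exposed.
- **That frequent step 1 rejection means false subgroup findings.** Step 2 follows and holds the final rate near 5%.

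**Conclusion.** The point holds as an under-specified procedure that goes wrong under the SAP's own stated coding.

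- **Two indicators:** modification common to PC and IT is declared about 5% of the time, against 73% to 94% for a direct test, for any factor. Separately, Model (3) effects for baseline BMI and other factors outside the explanatory terms are biased in proportion to the SD/UC slope.
- **Three slopes:** testing and estimation are sound. The remaining cost is the step 1 gate for factors outside the explanatory terms when slopes have opposite signs, 0.64 to 0.65 against 0.73 in one scenario.

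The powers and kilogram biases depend on assumed slopes, equal allocation, the 0.60 SDE and the assumed BMI-weight correlation. Two facts do not: equality of two active-arm gammas says nothing about shared modification, and a model without X fixes the control slope at zero. A reader should not infer that Aim 4 results are necessarily wrong, since that depends on how the analyst reads k. Aim 4 is secondary, and the primary comparisons are untouched.

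**What to change.** Replace the two-step sequence with one specification for each factor X:

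1. Fit Model (1) plus X (unless already among the explanatory terms) plus PC x X and IT x X, with SD/UC as reference.
2. Test both interactions equal to zero in a single 2-df test at two-sided 0.05, with no preliminary gate.
3. Take all subgroup estimates from that same model, at each level of a categorical factor or at the chosen percentiles of a continuous one.

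This is correct for every listed subgroup, whichever reading was intended. In simulation with a main effect only, the test rejects 4% to 5% of the time. It changes SAP wording only, has fewer steps than the present text, and needs no new data. If the sponsor prefers to keep two steps, the minimum is to state that k covers all three arms and to accept the small loss of power from the gate.
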